8. OUTCOMES

8.1 PRIMARY ENDPOINT

The primary endpoint of the study is BCTQ-SSS change at 3 months. The BCTQ is a CTS specific questionnaire that has been shown to be highly reproducible, internally consistent, valid, and responsive to clinical change in CTS and subject status post-CTR. The BCTQ includes a symptom severity score (BCTQ-SSS) and a functional status score (BCTQ-FSS). The BCTQ-SSS consists of 11 symptom severity questions. Scoring for the BCTQ- SSS ranges from 1 to 5, with higher scores indicating more severe symptoms, and is calculated as the mean of each response. The change in BCTQ-SSS score at the 3-month follow-up relative to baseline will represent the primary endpoint of the study.

8.2 SECONDARY ENDPOINTS

8.2.1 Time to Return to Normal Daily Activities

Time to return to normal daily activities will be ascertained through the ViedocMe ePRO module which asks whether the subject has returned to normal daily activities outside of work. Reminders will be sent to the subjects either by email or text messaging to minimize the risk of missing data. Time to return to normal daily activities postoperatively will represent a secondary endpoint of the study. The time to return to normal daily activities will be defined as the number of days between treatment and the time the subject reports returning to normal daily activities, irrespective of work status.

8.2.2 Time to Return to Work Among Employed Subjects

Among study subjects who report full-time or part-time employment, time to return to work will be ascertained through the ViedocMe ePRO module by asking whether the subject has returned to work in any capacity (full or limited). Reminders will be sent to the subjects either by email or text messaging to minimize the risk of missing data. Time to return to work postoperatively will represent a secondary endpoint of the study. The time to return to work will be defined as the number of days between treatment and the time the subject reports returning to work in any capacity.

8.2.3 BCTQ-FSS Change at 3 Months

The BCTQ-FSS additionally consists of 8 functional status questions (BCTQ-FSS). Scoring for the BCTQ-FSS ranges from 1 to 5, with higher scores indicating more functional limitation, and is calculated as the mean of each response. The change in BCTQ-FSS score at the 3-month follow-up relative to baseline will represent a secondary endpoint of the study.

8.2.4 MHQ Change at 3 Months

The Michigan Hand Questionnaire (MHQ) is a validated, hand-specific questionnaire consisting of 37 questions in 6 domains:

- overall hand function
- activities of daily living
- work performance
- pain
- aesthetics
- satisfaction

The raw score for each of the six domains is converted to a score ranging from 0-100, with 100 being the best score for each domain with the exception of the pain domain for which 100 = maximal pain. An overall MHQ score can be obtained by reversing the pain domain score (pain = 100 minus pain score), summing the scores for all six domains, then dividing by six. MHQ scores may be reported as overall scores or scores by each domain. For example, previous studies have documented a minimally clinically important difference of 13 for the overall function, 23 for the pain, and 8 for work domains. The MHQ has also been validated to use in patients with bilateral hand symptoms, such as bilateral CTS. The change in the total MHQ score as well as each of its 6 domains score at the 3-month follow-up relative to baseline will represent secondary endpoints of the study.

8.2.5 Numeric Pain Scale Change at 3 Months

Subjects will be asked to rate their wrist pain severity on a scale of 0 to 10, where 0 represents "no pain" and 10 represents "worst possible pain". The change in Numeric Pain Scale score at the 3-month follow-up relative to baseline will represent a secondary endpoint of the study.

8.2.6 EQ-5D-5L Change at 3 Months

The EuroQol 5-Dimension 5-Level (EQ-5D-5L) is a generic preference-based questionnaire developed by the EuroQol Group to measure health-related quality of life. The EQ-5D-5L measures quality of life across 5 domains: mobility, self-care, usual activities, pain/discomfort, and anxiety/depression. Each dimension is scored on a 5-level severity ranking consisting of: no problems, slight problems, moderate problems, severe problems, unable to/extreme problems. The change in EQ-5D-5L score at the 3-month follow-up relative to baseline will represent a secondary endpoint of the study.

8.2.7 Device- or Procedure-related Adverse Events at 3 Months

Adverse events (AEs) occurring within 90 days of treatment and that are adjudicated as definitely related or probably related to the device, or definitely related or probably related to the

procedure will be included in this endpoint. The incidence of device- or procedure-related AEs within 90 days of treatment will represent a secondary endpoint of the study.

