6.2.1 Inclusion Criteria

- 1. ≥ 18 years of age
- 2. Clinical diagnosis of unilateral or bilateral idiopathic CTS
- 3. CTS-6 score >12 in target hand*
- 4. Median nerve cross-sectional area ≥10 mm2 in the proximal carpal tunnel region of the target hand measured by diagnostic ultrasound*
- 5. Prior failure of one or more nonsurgical treatment options (e.g., physical activity modification, bracing, splinting, corticosteroid injection)*
- 6. Subject agrees to complete follow-up questionnaires over a 24-month period
- 7. Subject has a valid smart phone number and/or email address to receive and answer follow-up questionnaires

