9.3 RELATIONSHIP OF ADVERSE EVENTS TO THE DEVICE OR PROCEDURE

A description of how an AE relates to the study device or procedure will be reported on the Adverse Event CRF.

A device-related AE is directly attributable to the device or to improper use of the device. A procedure-related AE is directly attributable to the procedure, irrespective of the device, including complications from anesthesia or other procedures incidental to the main procedure.

The relationship of the AE to the device or procedure will be determined by the Investigator using the following definitions:

- Definite: The AE follows a reasonable temporal sequence from the time of the index procedure, which includes AEs that occur during the index procedure or during the follow-up period.
- Probable: The AE follows a reasonable temporal sequence from the time of the index procedure, and the possibility can be excluded that factors other than the index procedure, such as underlying disease, concomitant drugs, or concurrent treatment caused the AE.
- Possible: The AE follows a reasonable temporal sequence from the time of the index procedure and the possibility of index procedure involvement cannot be excluded. However, other factors such as underlying disease, concomitant medications, or concurrent treatment are presumable.

- Unlikely: The AE has an improbable temporal sequence from the time of the index procedure, or such AE can be reasonably explained by other factors, including underlying disease, concomitant medication, or concurrent treatment.
- Not related: The AE has no temporal sequence from the time of the index procedure, or it can be explained by other factors, including underlying disease, concomitant medication, or concurrent treatment.

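### The 90-day safety endpoint counts only definite and probable events, but the relatedness grades overlap and are not ordered, so the same nerve symptom can be counted or left out

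*Combined protocol and SAP*

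**What the plan says.** Section 8.2.7 defines the safety endpoint. It covers "Adverse events (AEs) occurring within 90 days of treatment" that are "adjudicated as definitely related or probably related to the device", and events graded definite or probable for the "procedure will be included in this endpoint". The other three grades (possible, unlikely, not related) are outside it.

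Section 9.3 defines the grades:

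- **Definite:** "Definite: The AE follows a reasonable temporal sequence from the time of the index procedure". The rest of the entry says only that the event may occur during the procedure or during follow-up. No alternative cause has to be ruled out.
- **Probable:** the same timing, and "the possibility can be excluded that factors other than the index procedure, such as underlying disease" (with concomitant drugs and concurrent treatment also listed), caused the event.
- **Possible:** the same timing, and "the possibility of index procedure involvement cannot be excluded", but "other factors such as underlying disease, concomitant medications, or concurrent treatment are presumable".

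Inclusion criterion 2 in section 6.2.1 is "Clinical diagnosis of unilateral or bilateral idiopathic CTS", so the underlying disease is present in every treated hand. Section 9 counts a worsening of a pre-existing condition after the incision as an adverse event. Section 9.6 gives the final grade to an independent medical reviewer. Section 10.2.3 plans counts, percentages and Clopper-Pearson intervals per subject. It does not plan a tabulation by relatedness grade or a count that includes possible events. Section 8.2.9 repeats related and serious related adverse events at other times without saying which grades qualify.

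**The concern.** The cut-off in 8.2.7 has a clear meaning only if the grades run in order from strong to weak attribution, and in 9.3 they do not. Definite is the least demanding of the three upper grades. The line between counted and uncounted events therefore depends on which definition the adjudicator turns to first.

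This matters most for new or worse numbness, weakness or hand pain. These are the events for which carpal tunnel syndrome is an obvious alternative explanation, and they are central to the safety of a procedure carried out next to the median nerve. The plan gives the adjudicator little help in separating the two causes. Nerve ultrasound and CTS-6 are scheduled at baseline only (section 7.2.2). After the procedure, adverse events reach the site through the subject's phone calls or wound images, with a clinic visit only where needed (section 9.5).

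The trial has one arm, so no concurrent rate shows how much of what is counted, or left out, is background. 8.2.7 is the only secondary endpoint for safety, and a reader could not tell from the reported rate how the overlap had been resolved.

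**Working it through.** **Step 1. Compare the grades for one event.** Take a new or worse median-nerve symptom that begins soon after the procedure in a hand with carpal tunnel syndrome.

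| Grade (9.3) | Timing condition | Other causes | Does the event fit? | Counted in 8.2.7? |
|---|---|---|---|---|
| Definite | plausible timing | no condition | yes | yes |
| Probable | plausible timing | must be excluded, including underlying disease | only if the disease can be ruled out | yes |
| Possible | plausible timing | thought likely; procedure not ruled out | yes, if the disease is a likely alternative | no |

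Any event that meets probable or possible also meets definite, because all three share the timing condition and definite adds nothing to it. The grades are therefore neither ordered nor mutually exclusive.

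**Step 2. Follow each way of applying the text.**

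- *Conventional hierarchy* (definite stricter than probable): the symptom cannot reach probable unless the disease is excluded. It falls to possible and is not counted. Events in which the procedure played a part can be missed.
- *Literal reading:* good timing is enough for definite, so the symptom is counted. Probable and possible then do no work, and some events caused by the disease are counted as definitely related.

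The documents do not say which reading applies, so the sign of any bias cannot be derived from them.

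**Step 3. Illustrate the size.** The plan states no expected rate, margin or performance goal for this endpoint, so there is no figure to reproduce. Inputs:

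- n = 140 subjects, the minimum enrolment in section 10.1.
- Clopper-Pearson intervals per subject, from section 10.2.3.
- No subject with a definite or probable event, and x subjects with a possible event as their worst grade. **Both counts are assumptions;** x runs from 0 to 7.

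For x subjects in n, the lower limit is the 0.025 quantile of Beta(x, n − x + 1) and the upper limit is the 0.975 quantile of Beta(x + 1, n − x). For x = 0 the lower limit is 0 and the upper limit is 1 − 0.025^(1/140) = 0.026.

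| Possible subjects added (assumed) | Rate | Exact 95% CI |
|---|---|---|
| 0 (definite/probable alone) | 0/140 = 0% | 0 to 2.6% |
| 1 | 1/140 = 0.7% | 0.02 to 3.9% |
| 3 | 3/140 = 2.1% | 0.4 to 6.1% |
| 5 | 5/140 = 3.6% | 1.2 to 8.1% |
| 7 | 7/140 = 5.0% | 2.0 to 10.0% |

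With the 15% attrition assumed in section 10.1, 140 × 0.85 = 119 subjects would remain. At that denominator, zero events give 0% (0 to 3.1%), one gives 0.8% (0.02 to 4.6%) and seven give 5.9% (2.4 to 11.7%). The pattern is the same.

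**Step 4. Check that few events are to be expected.** Section 5 reports one incomplete release among 346 registry patients with complication data (0.3%). It also reports one case of complex regional pain syndrome and no neurovascular injury in the office-based cohort. At counts this low, regrading a few subjects changes both the rate and its upper limit.

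**The case against.** A reader might infer more: that nerve symptoms will tend to be graded possible, and that the endpoint is therefore biased downward. The documents do not support this. Definite is a counted grade and needs only plausible timing, so a literal adjudicator would count these events. No data in the documents show how such symptoms are graded in practice. Section 9 requires a change from baseline, so unchanged symptoms of carpal tunnel syndrome are not adverse events, and nothing shows that an independent reviewer would blame a new deficit on the old disease. That part of the objection stands.

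A reader might also take 8.2.7 to be the only safety measure at 3 months. It is not: 8.2.9 lists serious related events at 3 months as an additional outcome. General adverse event reporting in 10.2.3 and the safety board's review in 9.7 are not limited to related events. Symptom severity, pain and function are measured without any attribution step.

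Three further points carry weight. A definite/probable cut-off is openly prespecified. Adding possible events brings in some caused by the disease, which could overstate harm when there is no control arm. And no success criterion depends on this endpoint, because success rests on BCTQ-SSS alone.

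These points limit the concern but do not remove it. The independent reviewer has to work from the same overlapping definitions. Mean symptom scores are not event rates. Total adverse event counts do not show what the cut-off left out, because no count by grade is planned. The risk of overstatement is an argument for reporting both counts, not for reporting only the narrower one.

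**Conclusion.** The concern holds as a defect in the definitions and in the reporting, not as a demonstrated bias. 8.2.7 cuts between grades that overlap. Because every treated hand has carpal tunnel syndrome, a well-timed nerve symptom can be counted or left out at the adjudicator's discretion. Understatement follows under a conventional hierarchy, and capture of these events follows under a literal reading. The direction is not established, and the number of events affected cannot be derived from the documents.

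Under the assumed counts, with 140 subjects and no definite or probable event, including one to seven possible subjects moves the rate from 0% to between 0.7% and 5.0%. The upper limit moves from 2.6% to between 3.9% and 10.0%. If no event is graded possible, nothing changes. The point affects how the safety result can be interpreted; it does not affect the primary endpoint.

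**What to change.** - **8.2.7:** report the per-subject 90-day incidence with exact 95% intervals in two lines, one for definite, probable and possible combined and one for definite and probable alone.
- **8.2.9:** state which grades qualify, and report the same two lines for the related and the serious related adverse event outcomes at each time point.
- **9.3:** reword the grades so that they are ordered and mutually exclusive. Definite should require at least what probable requires. Possible should take the well-timed events for which another cause is plausible and the procedure is not ruled out. The entries for unlikely and not related need the same tidying: each can be met through an alternative explanation alone, so a well-timed event could fall there too.
- **10.2.3:** add the two-line presentation to the adverse event analysis.

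The combined line does not depend on how the overlap among the upper three grades is resolved. The rewording is still needed for the narrower line and for the boundary with unlikely.

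The cost is a few sentences. Relationship is already recorded (9.5) and adjudicated (9.6), so no new data are needed, though any event already graded would have to be regraded under the new wording. The downside is a possibly less favourable combined rate that includes some events caused by the disease, which is why the narrower line should stay beside it.

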8.2.8 Global Satisfaction

Subjects will be asked to rate their satisfaction with the carpal tunnel release procedure and how likely they are to recommend their carpal tunnel release procedure to a friend or colleague.

8.2.9 Additional Outcomes

Additional outcomes of the study will include:

- BCTQ-SSS change at 2 weeks, 1 month, 6 months, 12 months, and 24 months
- BCTQ-FSS change at 2 weeks, 1 month, 6 months, 12 months, and 24 months
- MHQ change at 2 weeks, 1 month, 6 months, 12 months, and 24 months
- Numeric Pain Scale change at 2 weeks, 1 month, 6 months, 12 months, and 24 months
- EQ-5D-5L change at 2 weeks, 1 month, 6 months, 12 months, and 24 months
- Device- or procedure-related AEs at 2 weeks, 1 month, 6 months, 12 months, and 24 months
- Serious device- or procedure-related AEs at 2 weeks, 1 month, 3 months, 6 months, 12 months, and 24 months

9. ADVERSE EVENTS

An Adverse Event (AE) is defined as any adverse change (i.e., de novo or preexisting condition) from the subject's baseline medical condition occurring after the initial procedural incision has been initiated. Any AE which resolved and then recurred will be reported as a separate AE. A pre-specified listing of AEs will be documented on the Adverse Event eCRF.

9.1 SERIOUS ADVERSE EVENT

A serious adverse event (SAE) is defined as one that suggests a significant hazard or side effect, regardless of the relationship to the device or procedure. This includes, but may not be limited to, any event that:

- Results in death
- Is life threatening, or places the participant at immediate risk of death from the event as it occurred
- Requires or prolongs hospitalization
- Causes persistent or significant disability or incapacity
- Results in congenital anomalies or birth defects
- Is another condition which investigators judge to represent significant hazards

Important medical events may be considered serious by the investigator although they may not be immediately life threatening or result in death or prolong hospitalization. Such important medical events are those that may jeopardize the subject, require intervention to prevent one of the outcomes listed above, or result in urgent investigation. SAEs should be reported to the study Sponsor as soon as possible (24 hours recommended), but no more than 10 working days after the date the site becomes aware of the event.

Sites are also required to adhere to the reviewing IRB requirements for reporting of SAEs.

9.2 UNANTICIPATED ADVERSE DEVICE EFFECT

An unanticipated adverse device effect (UADE) is any serious adverse effect on the health or safety of a subject, any life-threatening problem or death caused by, or associated with a device, if such effect, problem, or death was not previously identified in nature, severity, or degree of incidence in the investigational plan (e.g., ICF, Study Protocol, Instructions for Use (IFU), publications, etc.), or any other unanticipated serious problem associated with a device that relates to the rights, safety, or welfare of subjects.

If an unanticipated adverse effect associated with the device occurs, the investigator shall notify the Sponsor and the IRB as soon as possible.

The Sponsor will investigate the event and notify the FDA and all other participating IRBs and investigators. Should the Sponsor determine that an unanticipated adverse effect presents an unreasonable risk to all participating subjects, the Sponsor will suspend the clinical investigation and notify all participating investigators, IRBs, country regulatory bodies and FDA.

9.3 RELATIONSHIP OF ADVERSE EVENTS TO THE DEVICE OR PROCEDURE

A description of how an AE relates to the study device or procedure will be reported on the Adverse Event CRF.

A device-related AE is directly attributable to the device or to improper use of the device. A procedure-related AE is directly attributable to the procedure, irrespective of the device, including complications from anesthesia or other procedures incidental to the main procedure.

The relationship of the AE to the device or procedure will be determined by the Investigator using the following definitions:

- Definite: The AE follows a reasonable temporal sequence from the time of the index procedure, which includes AEs that occur during the index procedure or during the follow-up period.
- Probable: The AE follows a reasonable temporal sequence from the time of the index procedure, and the possibility can be excluded that factors other than the index procedure, such as underlying disease, concomitant drugs, or concurrent treatment caused the AE.
- Possible: The AE follows a reasonable temporal sequence from the time of the index procedure and the possibility of index procedure involvement cannot be excluded. However, other factors such as underlying disease, concomitant medications, or concurrent treatment are presumable.

- Unlikely: The AE has an improbable temporal sequence from the time of the index procedure, or such AE can be reasonably explained by other factors, including underlying disease, concomitant medication, or concurrent treatment.
- Not related: The AE has no temporal sequence from the time of the index procedure, or it can be explained by other factors, including underlying disease, concomitant medication, or concurrent treatment.

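### In 9.3 the grade Definite tests timing only, so a well-timed AE with another likely cause fits both a grade that the 90-day related-AE endpoint counts and one that it does not (minor)

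*Combined protocol and SAP*

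**What the plan says.** Section 9.3 gives five grades and makes them the rule for grading: "The relationship of the AE to the device or procedure will be determined by the Investigator using the following definitions". Their tests are:

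- **Definite:** the entry reads "Definite: The AE follows a reasonable temporal sequence from the time of the index procedure, which includes AEs that occur during the index procedure", and its last clause runs on to follow-up: "which includes AEs that occur during the index procedure or during the follow-up period". There is no other condition.
- **Probable:** the same timing, and "the possibility can be excluded that factors other than the index procedure" caused the event.
- **Possible:** the same timing, and "the possibility of index procedure involvement cannot be excluded. However, other factors such as underlying disease, concomitant medications, or concurrent treatment are presumable".
- **Unlikely:** improbable timing, "or such AE can be reasonably explained by other factors, including underlying disease, concomitant medication, or concurrent treatment".
- **Not related:** no temporal sequence, "or it can be explained by other factors, including underlying disease, concomitant medication, or concurrent treatment".

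Just before the grades, 9.3 describes relatedness in general: "A device-related AE is directly attributable to the device or to improper use of the device". A parallel sentence covers the procedure.

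Section 8.2.7 makes the incidence of related AEs within 90 days a secondary endpoint and counts those adjudicated Definite or Probable. Section 8.2.9 lists related AEs, and serious related AEs, at other times without naming grades. Section 9.6 gives the final classification to an independent medical reviewer. Section 10.2.3 reports AEs per subject, with Clopper-Pearson intervals.

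**The concern.** A causality scale should give each event one grade, at least across the line that an endpoint draws. Here the highest grade has the weakest test among the three that need reasonable timing. Its timing test also reaches through follow-up, so any well-timed event can meet it, including one with a good alternative explanation. The plan does not say which grade prevails when two fit. Someone who applies Definite as worded would count events that the scale elsewhere places in Possible, Unlikely or Not related. At stake is the meaning of the related-AE incidence in a study whose purpose includes reporting safety.

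**Working it through.** The documents give no expected rate of AEs, so there is no planned figure to reproduce. The check is a comparison of the definitions, followed by the step size of the endpoint.

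**1. Which grades fit.** Cross three timing states (reasonable, improbable, none) with four states of other cause (excluded; unlikely but not excluded; presumable; explains the event). That gives 3 × 4 = 12 combinations. For Possible, procedure involvement is taken as not excluded. With reasonable timing:

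| Other cause | Grades met in 9.3 | Counted in 8.2.7? |
|---|---|---|
| Excluded | Definite, Probable | Yes, under both |
| Unlikely but not excluded | Definite | Yes |
| Presumable | Definite, Possible | Yes and no |
| Explains the event | Definite, Unlikely, Not related | Yes and no |

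The other eight combinations (improbable or no timing) meet only Unlikely, Not related or both, and none of these is counted. Five of the 12 combinations meet more than one grade, but three of the five cannot change the endpoint. Two can: reasonable timing with another cause presumable, and reasonable timing with another cause that explains the event.

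**2. Size of one reclassification.** Incidence is per subject and the planned minimum is 140 (section 10.1), so the step is 1/140 = 0.71 percentage points.

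**3. Illustration.** The counts x below are assumed. The exact limits are the 2.5% point of Beta(x, n − x + 1) and the 97.5% point of Beta(x + 1, n − x), with n = 140 and a lower limit of 0 when x = 0.

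| Subjects counted | Incidence | Exact 95% CI |
|---|---|---|
| 0 | 0.0% | 0 to 2.6% |
| 1 | 0.7% | 0.02 to 3.9% |
| 2 | 1.4% | 0.2 to 5.1% |
| 5 | 3.6% | 1.2 to 8.1% |
| 10 | 7.1% | 3.5 to 12.7% |

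The table shows how the result would move for a given number of ambiguous subjects. It does not estimate that number.

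**The case against.** The strongest reply is that 9.3 must be read whole. Its lead-in ties a related AE to direct attribution, so an event explained by underlying disease would not be called definitely related, however well timed. Section 8.2.7 counts adjudicated events, and a single independent reviewer has the final word, so sites should not drift apart. With one arm, misgrading cannot bias a comparison between arms.

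Much of this stands. The intended reading is fairly clear and the practical risk is reduced, which is why the point is minor. It does not remove the defect. The lead-in is part of none of the five grades and does not say which prevails. If it governed them all, Possible, which presumes other factors, would make little sense. Section 9.6 supplies neither definitions nor a rule for an event that fits two grades. Consistent use of an overlapping scale still leaves the counted set undefined.

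A reader might also infer an undercount, because the alternative limbs of Unlikely and Not related could remove events in which the procedure played a part. The documents do not support this as a finding. An event with both a procedural and another presumable cause fits Possible, which 8.2.7 leaves out by choice, and nothing shows that events would move down from Definite or Probable.

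**Conclusion.** The point holds as a minor one: 9.3 is wrong as written, and followed literally it overcounts. Two situations meet both a counted and an uncounted grade. The effect is confined to the descriptive endpoint in 8.2.7, and to the related-AE outcomes in 8.2.9 if the same grades carry over, which is the natural reading. Its size is unknown, at about 0.7 percentage points per reclassified subject if 140 are analysed. The primary endpoint and the success rule in 10.2.3 do not use these grades, and 9.1 defines an SAE whatever its cause.

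Three stronger readings are tempting but unsupported:

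- A reader might infer that the endpoint is distorted because Definite is easier to meet than Probable. Both are counted, so that inversion alone cannot change the pooled count.
- A reader might take the prior complications in section 5 (1 of 346 registry patients, 1 of 88 office-based patients) as a sign that one ambiguous event would double the result. Those cases were an incomplete release and a complex regional pain syndrome. Neither is shown to be of ambiguous cause, so they do not estimate how many subjects are affected.
- A reader might infer that the whole scale needs rewriting. Changing one grade settles both situations.

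**What to change.** Reword Definite so that it has three conditions: the present timing test (during the procedure or follow-up); direct attribution to the device or procedure; and no other factor that is presumable as the cause or explains the event. Leave Probable and the other grades as they are. Then state that:

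- an event with another presumable cause is graded Possible;
- an event explained by another cause is graded Unlikely or Not related;
- the independent medical reviewer uses the same definitions as the investigator.

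On the grid above, both straddling combinations then fall only in uncounted grades. Well-timed, attributable events with no presumable other cause stay counted. One remaining combination needs a sentence: good timing, direct attribution not established, and other causes unlikely but not excluded. It now fits Definite on timing alone and would fit no grade under the new wording, so the amendment should name its grade.

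The cost is a wording amendment, with the IRB submission and distribution to sites that 11.9.2 requires. Any AEs already graded Definite need a check. Because the study is open and single-arm, the independent reviewer should apply the new wording to all of them, not a selection, and document every change. No new data are needed, since 9.5 already records relationship for each AE.
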